### 7.3 Duration of Participation

Describe how long subjects will be involved in this research study. Include the number of sessions and the duration of each session - consider the total number of minutes, hours, days, months, years, etc.

Total duration of participation will be approximately 4 months. Active participation is only required during their initial post TACE treatment imaging visit and the imaging performed 2-4 months post TACE treatment.

### 7.4 Test Article(s) (Study Drug(s) and/or Study Device(s))

#### 7.4.1 Description

Provide a brief description of all test articles (drugs (including any foods and dietary supplements), devices and/or biologics used in the research including the purpose of their use and their approval status with the Food and Drug Administration (FDA). Include information about the form of the drug product (e.g., tablets, capsules, liquid).

Contrast enhanced ultrasound utilizes standard ultrasound units with a contrast software package included on the machine. The test utilizes Lumason (Bracco), which comes in a sterile vial as a powder. It is reconstituted at the time of use with sterile saline (provided in the Lumason package). Each kit provides the equivalent of two liver doses (2.4 mL each). The reconstituted liquid Lumason is then injected intravenously, followed by a flush with sterile saline (5-10 mL saline after each Lumason dose). Lumason is FDA approved for liver lesion evaluation in adults, which is what this study is evaluating (specifically, liver lesions in patients with hepatocellular carcinoma after treatment). After TACE treatment, the liver lesion may shrink, but does not entirely disappear, so contrast ultrasound will be evaluating the residual lesion that is left – is there residual viable tumor left, or not.

#### 7.4.2 Treatment Regimen

Describe dose, route of administration and treatment duration. Include information about dose adjustments.

Intravenous injection of Lumason, 2.4 mL dose (standard liver dose, FDA approved), followed by saline flush. Each vial of Lumason comes with two doses included. This will be administered as in standard of practice of the radiology department at Penn State Health.

#### 7.4.3 Method for Assigning Subject to Treatment Groups

Describe the randomization process and how the associated treatment assignment will be made.

All subjects will receive the CEUS.

#### 7.4.4 Subject Compliance Monitoring

Insert the procedures for monitoring subject compliance.

PI will provide oversite by monitoring data monthly for enrollment, adverse events.

#### 7.4.5 Blinding of the Test Article

Describe how the test article is blinded.

Not applicable

#### 7.4.6 Receiving, Storage, Dispensing and Return

Lumason will be used per the FDA label and as standard of care in the radiology department at Penn State Health

##### 7.4.6.1 Receipt of Test Article

Describe how the test article will be obtained and from what source. Describe how the study test article will be packaged along with amounts (e.g., number of tablets/capsules or volume of liquid) and labeling. If drug kits are used, describe all the contents of the kit and associated labeling.

Not applicable.

##### 7.4.6.2 Storage

Describe the plans to store, handle the test article so they will be used only on subjects and only by authorized investigators. Describe storage temperature requirements and how temperature will be monitored and recorded.

Not applicable.

##### 7.4.6.3 Preparation and Dispensing

Describe how the test article will be assigned to each subject and dispensed. Describe the steps necessary to prepare the test article. Include where the test article preparation will be done and by whom. Fully describe how the study treatment is to be administered and by whom.

Not applicable.

##### 7.4.6.4 Return or Destruction of the Test Article

Describe the procedures for final reconciliation of the test article supply at the end of the study and whether the test article is to be shipped back to a source or destroyed on site.

Not applicable

##### 7.4.6.5 Prior and Concomitant Therapy

Describe what prior and/or concomitant medical therapy will be collected. Describe which concomitant medicines/therapies are permitted during the study. Describe which concomitant medicines are not permitted during the study.

No limitations on other medications patients may take.

### 8.0 Subject Numbers and Statistical Plan

#### 8.1 Number of Subjects

Indicate the maximum number of subjects to be accrued/enrolled. Distinguish between the number of subjects who are expected to be enrolled and screened, and the number of subjects needed to complete the research procedures if applicable (i.e., numbers of subjects excluding screen failures.)

We plan to enroll 34 subjects.

#### 8.2 Sample size determination

If applicable, provide a justification of the sample size outlined in section 8.1 to include reflections on, or calculations of, the power of the study.

Planned sample size = 34

Presently there is no data available to suggest how large an effect size may exert on the primary outcome measures. Accordingly, a formal sample size calculation was not done as the goal of this pilot study is to: 1) assess the feasibility of the study design, 2) generate data needed for a formal power calculation, and 3) generate pilot data for larger-scale grant submission. Based on the availability of patients, feasibility of our operations, we plan to recruit 34 patients. We believe this sample will serve our purpose well as a pilot study with plans to include further patients as funding allows.

### 8.3 Statistical methods

Describe the statistical methods (or non-statistical methods of analysis) that will be employed.

Patient demographics and major clinical information described above will be summarized using descriptive statistics. The main outcome variables in primary objective are the incidence of residual tumor and new tumor, which are both binary. The rate of residual/new tumors using CEUS and CT/MRI will be compared using McNemar's test, which is suitable for comparing paired binary variables. The point estimate and 95% confidence interval (CI) of the incidence rate for CEUS and CT/MRI will be reported separately. Due to the limited sample size of this pilot study, the non-inferiority between CEUS vs CT/MRI will be evaluated just by comparing the CIs of the incidence rate for each method, not by a formal statistical non-inferiority test which requires a much larger sample size. A few additional subgroup analyses will be performed to see if the incidence rate varies by stratification (such as BMI group, liver disease type). Due to the exploratory nature of this study no multiple regression models will be used, and no adjustment of the alpha rate will be made due to multiple testing. Treating the CT/MRI as the clinical gold standard, the sensitivity and specificity of CEUS will be estimated with their 95% CIs. The data from secondary objective will be analyzed similarly as those for the primary objective. For tertiary objective, the subjective ratings from patients between the CT/MRI and ultrasound will be compared using nonparametric Wilcoxon Signed-rank tests. The ratings may be further correlated with some of the baseline demographic and clinical factors using nonparametric Kruskal-Wallis tests. All analyses will be performed using statistical software SAS version 9.4 or higher (SAS Institute, Cary, NC, USA). All tests are two-sided and the significance level to be used is 0.05.

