## 1.0 Objectives

### 1.1 Study Objectives

Describe the purpose, specific aims or objectives. State the hypotheses to be tested.

In this study, we propose a prospective trial to determine if contrast enhanced ultrasound (CEUS) is non-inferior to CT or MRI in patients with hepatocellular carcinoma (HCC) following transcatheter arterial chemoembolization (TACE) treatments, in a U.S. population, using Lumason contrast agent. This would be the largest trial to date examining this patient population in the U.S.

The primary objective of our study is to estimate the sensitivity and specificity of the CEUS (Research Timepoint 1) and evaluate for non-inferiority between CEUS and the clinical gold standard of CT/MRI using the Liver Reporting & Data System (LIRAD). We will be assessing the presence of treated or residual tumor, new sites of disease, and portal vein thrombus. Patient factors, such as BMI, underlying liver disease type, alpha fetoprotein level, and size of liver will be recorded. If findings of metastatic disease external to the liver are identified on CT or MRI and not seen on CEUS, they will be recorded.

CEUS, like regular ultrasound, only images specific organs and cannot identify necessarily metastatic disease, as ultrasound cannot image bones and lungs for this purpose.

The second objective of the project will compare the CEUS with a second, standard of care, follow-up CT or MRI (performed 2-4 months later [Research Timepoint 2]). CT can have false negatives due to ethiodol obscuring subtle, early disease and it is possible that CEUS could identify residual disease earlier compared to the gold standards, but would be characterized as a false positive if compared only to the initial imaging (Timepoint 1). This follow-up will evaluate for false positives or negatives on any of the modalities.

The third objective of the project will evaluate patient subjective data in regards to imaging modality preference and possible effects on compliance. The survey will be administered at the conclusion of Timepoint 1 and will include questions about anxiety, comfort, compliance, and modality preference, graded on a Likert scale.

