### 1.2 Primary Study Endpoints

State the primary endpoints to be measured in the study.

Clinical trials typically have a primary objective or endpoint. Additional objectives and endpoints are secondary. The endpoints (or outcomes), determined for each study subject, are the quantitative measurements required by the objectives. Measuring the selected endpoints is the goal of a trial (examples: response rate and survival).

- Non-inferiority between CEUS and the patient's routine CT/MRI, which occurs 2-4 months after TACE treatment (Research timepoint 1). Additionally endpoints that will be measured include treated, residual, or new tumor present on the follow-up.
- The second routine follow-up of CT/MRI (timepoint 2) will be compared to exclude false positives/negatives in the first follow-up imaging (timepoint 1), which occurs approximately 2-months after the first imaging visit.
- Patient subjective data – through the use of a patient survey, given after the first follow-up (Research timepoint 1), where patient had CEUS and CT/MRI (2-4 months after TACE treatment).

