### 1.3 Secondary Study Endpoints

State the secondary endpoints to be measured in the study.

To determine if patient or tumor characteristics (BMI, pre-treatment alpha feta protein levels, size of tumor treated) are predictive of whether CEUS is non-inferior to CT/MRI or in which cases it may not be, due to the limitations of ultrasound as a modality.

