**7.1 Study Design**

Describe and explain the study design.

This is a prospective trial to determine if contrast enhanced ultrasound (CEUS) is non-inferior to CT or MRI in patients with hepatocellular carcinoma (HCC) following transcatheter arterial chemoembolization (TACE) treatments. All patients will receive standard of care CT/MRI and will also get a contrast ultrasound to directly compare.

Timepoint 0: You agree to take part in the study at the time of your first TACE treatment.

Timepoint 1:  
• CT or MRI and CEUS  
• Complete short survey

Timepoint 2: Return for follow-up standard of care imaging (either a CT or MRI).

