### 11.2 Potential Benefits to Others

Include benefits to society or others.

If CEUS is shown to be non-inferior to CT/MRI, there would be several different benefits to future patients (and potentially the subject themselves, in follow-up) –

This study has the potential to specifically affect patients with cirrhosis or other liver diseases who have been diagnosed and treated for HCC, often used as a bridge to transplantation. Four phase CT and contrast enhanced MRI are the standard methods for establishing the success of TACE treatment by looking for residual disease and for new tumor, but may be contraindicated or not feasible in certain patients. CEUS has a safer overall risk profile and is also significantly less expensive than CT or MRI. Contrast reactions are rare in CEUS, the exam has less contraindications than CT or MRI. Additionally, multiple separate doses can be administered in CEUS to get a second or better look at an area of concern in the liver.

Intrinsically, ultrasound has high spatial resolution and has a potential for identifying residual or recurrent tumor at the same rates and potentially even earlier than a CT scan can, where ethiodol can obscure subtle signs of residual tumor (23). This would ensure that HCC patients are triaged appropriately and potentially decreases morbidity with a safe, accurate, and less expensive bridge to liver transplantation.

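### Non-inferiority is judged by comparing two separate tumour-rate intervals, with no margin or rule, so missed tumours can cancel against false positives

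*Combined protocol and SAP*

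**What the plan says.** Section 7.1 states the purpose: "This is a prospective trial to determine if contrast enhanced ultrasound (CEUS) is non-inferior to CT or MRI". Section 1.1 words the primary objective as follows: "estimate the sensitivity and specificity of the CEUS (Research Timepoint 1) and evaluate for non-inferiority between CEUS and the clinical gold standard of CT/MRI". The first primary endpoint in 1.2 is "Non-inferiority between CEUS and the patient's routine CT/MRI, which occurs 2-4 months after TACE treatment". The secondary endpoint in 1.3 asks which patient or tumour characteristics "are predictive of whether CEUS is non-inferior to CT/MRI".

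Section 8.3 says how this will be decided. The main outcomes are residual tumour and new tumour, both binary. Each modality's rate is reported with its own 95% CI, and "the non-inferiority between CEUS vs CT/MRI will be evaluated just by comparing the CIs of the incidence rate for each method". The section attributes this to the small pilot sample and rules out a formal non-inferiority test. No margin, bound or reading rule appears in 1.1, 1.2, 1.3, 7.1, 8.2 or 8.3.

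The same section plans McNemar's test on the two rates. It also says that, against CT/MRI, "the sensitivity and specificity of CEUS will be estimated with their 95% CIs". Neither is linked to the non-inferiority judgement, and no target is set for sensitivity or specificity.

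**The concern.** There are three separate faults.

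- **No decision rule.** Two analysts could follow 8.3 faithfully and reach opposite conclusions from the same data.
- **The pairing is lost.** Every patient has both examinations, but two separate intervals do not use that.
- **The quantity is not accuracy.** A tumour missed in one patient and a false call in another leave the CEUS rate unchanged. McNemar's test compares the same two marginal rates, so it has the same blind spot.

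The report could therefore call CEUS non-inferior beside sensitivity and specificity figures that show it performing badly, and nothing says which governs. Section 11.2 makes the benefit to future patients depend on this conclusion ("If CEUS is shown to be non-inferior to CT/MRI, there would be several different benefits to future patients"), and 8.2 intends the data for a larger grant submission. Enrolled patients' care is not affected: under 7.2.2 and 12.0 the CEUS result is neither reported in the medical record nor shared with subjects.

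**Working it through.** **Inputs.** n = 34 paired patients (8.1, 7.1) and two-sided 0.05 (8.3). The sample size rests on availability and feasibility, so there is no power figure to reproduce. The documents give no prevalence of residual or new tumour, so I assume 10, 17 or 24 CT/MRI positives. Intervals are Clopper-Pearson. With b misses and c false positives, asymptotic McNemar is (b − c)²/(b + c) on 1 df. The exact version is a two-sided binomial test of b out of b + c at 0.5.

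**1. Balanced errors, under any rule for comparing the intervals.** Take 17 positives, b = 10, c = 10. The CEUS count is 17 − 10 + 10 = 17. Both rates are 17/34 (32 to 68%), exactly as with perfect agreement, and McNemar p = 1.0. Sensitivity is 7/17 and specificity is 7/17: 41% (18 to 67%).

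**2. Misses only, if success means that the intervals overlap.**

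| CT/MRI positive (95% CI) | Most misses with overlap | CEUS positive (95% CI) | Sensitivity | Exact McNemar p |
|---|---|---|---|---|
| 10/34 (15.1–47.5%) | 9 | 1/34 (0.1–15.3%) | 10% | 0.004 |
| 17/34 (32.4–67.6%) | 11 | 6/34 (6.8–34.5%) | 35% | 0.001 |
| 24/34 (52.5–84.9%) | 12 | 12/34 (19.7–53.5%) | 50% | 0.0005 |

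**3. Misses only, stricter reading (CEUS estimate inside the CT/MRI interval).**

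| CT/MRI positive | Most misses that pass | CEUS rate vs CT/MRI lower limit | Sensitivity | McNemar p, asymptotic / exact |
|---|---|---|---|---|
| 10 | 4 | 17.6% vs 15.1% | 60% | 0.046 / 0.125 |
| 17 | 5 | 35.3% vs 32.4% | 71% | 0.025 / 0.063 |
| 24 | 6 | 52.9% vs 52.5% | 75% | 0.014 / 0.031 |

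**4. How often this would happen.** Simulation, 20,000 trials per setting, true sensitivity 60%:

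- Specificity 100%, prevalence 50%: the intervals overlap in 98 to 99% of trials. McNemar is significant in about 93% (asymptotic) or 70% (exact), so it usually gives warning.
- Specificity 80%, prevalence 50%: the intervals overlap in 99.8%. McNemar is non-significant in about 84% (asymptotic) or 89% (exact).
- Specificity 80%, other prevalences: asymptotic McNemar is non-significant in 95% at 30% prevalence and 38% at 70%.

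**5. What 34 patients can show.** If CEUS found every tumour, the lower 95% limit of sensitivity would be 0.025^(1/m): 69%, 80% and 86% for m = 10, 17 and 24.

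For a paired non-inferiority comparison of rates with true difference 0, n = ψ(1.960 + 0.842)²/δ², where ψ is the discordant proportion and δ the margin. Assuming δ = 0.10 and ψ = 0.1, 0.2 or 0.3, 80% power needs 79, 157 or 236 patients. At n = 34 the power is 45%, 26% or 19%. The plan is right that a formal test needs more patients in these cases.

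**6. Would a paired difference cure it?** No. In case 1 the difference is 0, with a Tango 95% CI of −25% to +25%. The interval uses the pairing and shows the imprecision, but the opposite errors still cancel in the estimate.

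**The case against.** The plan is open about its limits. It calls itself a pilot, says no formal test will be done, and gives its goals in 8.2 as feasibility, pilot data and to "generate data needed for a formal power calculation". Accuracy is named first in the primary objective and is analysed with intervals, so any report following 8.3 would show poor accuracy beside the rates. McNemar's test flags every overlap case in step 2 and, in its asymptotic form, every case in step 3. Ten misses with ten false positives is worse than chance: with 17 positives and 17 negatives, at least ten of each has probability of about 0.8% if true sensitivity and specificity are both 60%. The second objective also rechecks errors against Timepoint 2 imaging, because CT may miss early disease.

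Much of this stands. The step 1 case shows what the criterion allows, not what to expect, and step 4 is the more realistic guide. Pilot status explains the missing test and power. It does not explain choosing a rate as the quantity, or leaving out a reading rule while 1.1, 1.2 and 7.1 keep non-inferiority as the aim. McNemar gives no warning when errors run both ways, and a non-significant difference in 34 patients does not show non-inferiority. The Timepoint 2 comparison is a separate objective: 1.1 places the primary accuracy estimates at Timepoint 1, and the change proposed here leaves that second objective untouched.

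**Conclusion.** The concern holds and should be fixed before analysis. The sole criterion for the first-listed primary endpoint has no decision rule and uses a quantity that cannot distinguish perfect agreement from 41% sensitivity and specificity. That result needs no assumption about how the intervals are compared, only the illustrative split of 17 positives and 17 negatives. The tolerated misses in steps 2 and 3 depend on the reading assumed for an unstated rule. The simulated frequencies depend on assumed prevalence and accuracy. The defect is in the non-inferiority criterion, not the whole plan: the analysis that would expose the problem is already planned but is not given authority over the conclusion.

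**What to change.** In 8.3, delete the sentence on comparing the intervals and put in its place text such as:

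> CEUS will be cross-classified against CT/MRI at Timepoint 1 in a 2×2 table, separately for residual tumour and for new tumour, and all four cell counts will be reported. The primary conclusion rests on sensitivity and specificity from these tables with exact 95% CIs. McNemar's test and the paired rate difference with a paired 95% CI (for example Tango) are supplementary, because opposite errors cancel in both. No non-inferiority conclusion will be drawn from this pilot.

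In 1.1, 1.2 and 7.1, restate the aim as estimating accuracy and agreement in a pilot, and align the term in 1.3. Section 11.2 is conditional and can stand if read as referring to later work. The cell counts also supply the discordance figures that the power-calculation aim in 8.2 needs.

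The cost is wording in five sections, with no new patients, data or procedures. The study's stated claim becomes less ambitious.

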### 2.2 Previous Data

Describe any relevant preliminary data.

In unpublished work (CATS IRB STUDY00014728) presented at the 2019 Society of Radiologists in Ultrasound annual national meeting, our group presented on our experience in imaging liver patients with CEUS (19). At the time of presentation, 62 patients had been imaged, with 16% yielding a positive finding. Our group correctly diagnosed all lesions – all malignant lesions and vascular thrombi had confirmation via gold standard imaging of CT or MRI, or on explanation; benign lesions were confirmed by stability on follow-up imaging. Our study also evaluated patient factors that resulted in limited visualization with CEUS, which included severe steatosis and/or increased abdominal adiposity. In addition, at our institution, we have utilized CEUS in several patients post-TACE, which were subsequently shown to correctly diagnosis residual tumor by follow-up MRI and/or TACE (unpublished). If one were able to accurately and reliably use CEUS to determine residual tumor after TACE, this would decrease the need for CT scans (which have the risk of radiation and contrast-enhanced nephropathy) and MRI scans (which are very expensive and are difficult to perform in patients with claustrophobia).

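### Section 1.3 asks where CEUS may fall short of CT/MRI, but the only stratified imaging analysis in 8.3 is of the tumor incidence rate, which can hide misclassification

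*Combined protocol and SAP*

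**What the plan says.** Section 1.3 contains one secondary endpoint: whether BMI, pre-treatment AFP and the size of the treated tumor "are predictive of whether CEUS is non-inferior to CT/MRI or in which cases it may not be".

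Section 8.3 defines the main outcomes as the incidence of residual tumor and of new tumor, both binary. On strata it says only: "A few additional subgroup analyses will be performed to see if the incidence rate varies by stratification (such as BMI group, liver disease type"). Other sentences in 8.3 bear on the point:

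- Non-inferiority "will be evaluated just by comparing the CIs of the incidence rate for each method", without a formal test.
- McNemar's test, and the sensitivity and specificity of CEUS against CT/MRI, are planned with no stratum mentioned.
- "Due to the exploratory nature of this study no multiple regression models will be used".
- "The data from secondary objective will be analyzed similarly as those for the primary objective".
- Kruskal-Wallis tests relate baseline factors to the patients' survey ratings, not to imaging results.

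Section 1.1 gives the meaning of the second objective: "The second objective of the project will compare the CEUS with a second, standard of care, follow-up CT or MRI". It also states: "Patient factors, such as BMI, underlying liver disease type, alpha fetoprotein level, and size of liver will be recorded". Section 7.2 adds tumor characteristics and both imaging results to the recorded data.

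**The concern.** The endpoint in 1.3 is about CEUS performance relative to CT/MRI in the same patient. The planned subgroup analysis is about how often tumor is found. These are different quantities, and the second does not determine the first.

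The question is not incidental. Section 2.2 reports from the group's own experience "patient factors that resulted in limited visualization with CEUS, which included severe steatosis and/or increased abdominal adiposity", and section 2.3 names abdominal adiposity as a threat to CEUS accuracy in U.S. patients. The 1.3 endpoint is where the plan would show in whom CEUS falls short. If 8.3 is followed as written, a report could show equal tumor rates in a stratum where many patients are misclassified. That would be read as reassurance.

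**Working it through.** **No plan figure to reproduce.** Section 8.2 sets 34 patients on feasibility, with no effect size, margin or power. The counts and accuracies below are assumptions chosen for illustration.

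**Step 1. Match the question to the analyses in 8.3.**

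| Analysis in 8.3 | By stratum? | Answers 1.3? |
|---|---|---|
| Incidence rate of residual/new tumor | Yes (BMI group and liver disease type as examples) | No: a marginal rate |
| McNemar's test, CEUS vs CT/MRI | Not stated | No |
| Sensitivity and specificity | Not stated | No |
| Comparison of each method's CI | Not stated | No |
| Multiple regression | Excluded | No |
| Kruskal-Wallis | By baseline factors | No: survey ratings |

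The sentence on the secondary objective does not fill the gap. Section 1.1 makes the second objective the timepoint 2 comparison, and the next sentence of 8.3 calls the survey the tertiary objective. AFP and tumor size are not named in 8.3, but the list is open-ended, so they are unlisted and not excluded.

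**Step 2. Cancellation, with both methods' rates shown per stratum (the natural reading).** Assume 34 = 17 + 17 by BMI and 7/17 CT/MRI-positive in each stratum.

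| | TP | FN | FP | TN | CT/MRI positive | CEUS positive | Discordant |
|---|---|---|---|---|---|---|---|
| Low BMI | 7 | 0 | 0 | 10 | 7/17 | 7/17 | 0/17 |
| High BMI | 4 | 3 | 3 | 7 | 7/17 | 7/17 | 6/17 |

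All four rates are 7/17 = 41% (exact 95% CI 18.4% to 67.1%). Exact McNemar in high BMI, 3 against 3, gives p = 1.0. Discordance is 0/17 (exact CI 0% to 19.5%) against 6/17 (14.2% to 61.7%), Fisher p = 0.018.

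**Step 3. Exact cancellation is not required.** With 7 positives and 10 negatives, CEUS and CT/MRI counts differ by |FN − FP|. Take FN ~ Bin(7, 1 − Se), FP ~ Bin(10, 1 − Sp), independent.

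| Se / Sp | P(counts equal) | P(differ by at most 1) |
|---|---|---|
| 57% / 70% | 20% | 56% |
| 70% / 70% | 19% | 53% |
| 70% / 85% | 22% | 61% |
| 95% / 95% (comparator) | 50% | 91% |

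The difference in rates carries some information about accuracy, but a poor reader often produces counts within one patient of CT/MRI.

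**Step 4. Pure loss of sensitivity, no cancellation.** Assume prevalence 40%, Sp 95%, and Se 95% in one stratum and 50% in the other.

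- CEUS-positive rate: 0.4 × 0.95 + 0.6 × 0.05 = 0.41 against 0.4 × 0.50 + 0.6 × 0.05 = 0.23.
- In the poor stratum: FN = 0.4 × 0.50 = 0.20, FP = 0.6 × 0.05 = 0.03.

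With 17 per stratum, two-sided 0.05:

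| Comparison | Chance of showing a difference |
|---|---|
| Fisher across strata, CEUS rate 0.41 vs 0.23 | 11% |
| Exact McNemar within the poor stratum | 7% |
| Uncorrected asymptotic McNemar within the poor stratum | 29% |
| Separate CIs do not overlap: exact / Wilson / Wald | 0.2% / 0.8% / 3% |

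Overlap of separate intervals is an insensitive rule at this size. With CT/MRI at 7/17, suppose CEUS finds only 1 of the 7 tumors (1/17). The exact intervals are 0.1% to 28.7% and 18.4% to 67.1%; the Wilson intervals are 1.0% to 27.0% and 21.6% to 64.0%. Both pairs overlap. Wald intervals would separate here, but 8.3 does not name its CI method.

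**Step 5. If only one method's rate is compared across strata.** Hold CEUS accuracy at 90%/90% and let prevalence be 20% and 60%. The CEUS rate is 0.2 × 0.9 + 0.8 × 0.1 = 26% against 0.6 × 0.9 + 0.4 × 0.1 = 58%. A difference in prevalence alone would look like a difference in performance. This arises only on this narrower reading.

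**The case against.** The strongest reply is that 8.3 itself evaluates non-inferiority through incidence rates, so stratifying that rate follows the plan's own definition. Cancellation also affects the full-sample comparison. That is true. But in the full sample 8.3 also gives sensitivity and specificity, which expose the errors; by stratum it states neither.

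The section labels also conflict. Section 1.2 lists the timepoint 2 comparison among primary endpoints, and only 1.3 is headed secondary, so the sentence on the secondary objective could be stretched to cover 1.3. The order of 8.3 favors the timepoint 2 reading, and even when stretched the sentence names no stratification.

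Balanced errors are a constructed case, since limited visualization suggests missed tumors more than matched losses. This is fair; Step 4 covers the one-sided case. There the low power partly reflects 34 patients, and comparing discordance across strata (5% vs 23%) has only about 18% power itself. The advantage of the proposed table is that it shows the errors, not that it tests them better.

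Finally, selection limits what any table can show. BMI is capped at 40 (3.1), patients whose tumor was not seen on a recent ultrasound are excluded (3.2), and those whose lesion is not visible at timepoint 1 are removed (3.3.1). Failures through non-visualization leave before any cross-tabulation, and the strata may total fewer than 34. This stands as a limit on the remedy. It does not make incidence the right subgroup outcome.

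**Conclusion.** The concern holds. A stated secondary endpoint has a stated analysis that does not answer it. This is more than missing detail, because the outcome named for the subgroups is a different quantity from the one the endpoint asks about. On the reading most favorable to the plan, both methods can read 7/17 in a stratum where 6 of 17 patients are misclassified. A sensitivity of 50% would seldom be separated by the planned comparisons: 7% to 29% by McNemar if it were run within the stratum, and about 0.2% to 3% by separate CIs.

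These sizes rest on an assumed equal BMI split with all 34 patients evaluable, about 40% CT/MRI-positive, and independent errors in Step 3. The mismatch between 1.3 and 8.3 rests on the text alone. It should be corrected. It affects a secondary endpoint of a pilot and changes no stated figure.

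**What to change.** Add to 8.3, in substance:

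> For the secondary endpoint in 1.3, CEUS will be cross-tabulated against CT/MRI at timepoint 1 by BMI, pre-treatment AFP and treated-tumor size, using cut-points fixed before analysis. Discordant counts (false negatives, false positives), sensitivity and specificity will be reported per stratum with exact 95% CIs. These results are descriptive.

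A count, by the same strata where available, of patients removed under 3.3.1 because the lesion was not visible would help readers interpret the tables.

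The cost is two or three sentences and cut-points for three variables. No new data are needed: 1.1 records BMI and AFP, and 7.2 records tumor characteristics and both imaging results.

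The drawback is imprecision. A sensitivity of 4/7 has an exact 95% CI of 18% to 90%, a specificity of 7/10 has 35% to 93%, and 2/17 discordant has 1.5% to 36.4%. Even in the illustration, sensitivity of 7/7 against 4/7 gives Fisher p = 0.19 and specificity of 10/10 against 7/10 gives p = 0.21. The text should therefore say plainly that the tables describe where CEUS and CT/MRI disagree and do not test it.
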